7.2.4 Evaluable Population

Subjects who receive scheduled investigational product and are followed according to the protocol until Day 85 will constitute the Evaluable Population; however, subjects who receive at least one dose but discontinue treatment prior to receiving complete treatment regimen due to safety reasons will also be included in the Evaluable Population. Treatment classification in evaluable population will be on 'as-treated' basis.

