4.5.4.1 Modification of Treatments for RA

All changes to the RA treatment and the reasons for change must be clearly documented in the eCRF.
MedImmune CAM-3001 **Methotrexate and Corticosteroids**

Changes in ongoing RA treatment or introduction of new therapies are not allowed during the study period (Screening until Day 85). This includes the dose of methotrexate, corticosteroids and NSAIDS. After the Day 85 study visit, where possible the doses of background medication should be kept as constant as possible up to completion of the safety follow-up period (Day 169). Modifications to background RA medication will be permitted for safety reasons such as adverse reactions due to these medications (eg, gastrointestinal adverse events), and infectious diseases.

Subjects who require a change to their RA therapies for reasons other than safety, such as for poor disease control or worsening of their RA between Day 1 and Day 85 may be discontinued from dosing upon review by the medical monitor, but will remain in the study and be followed-up for safety. All study assessments should be completed, unless consent is withdrawn.

The risk/benefit to the subject should be carefully assessed and consideration given to the timing of any necessary dose modification or introductions of new medications during the study period and should be discussed with the medical monitor where possible.

Injection of IA corticosteroids is discouraged, but a maximum of 2 IA injections of corticosteroids (dose up to 40 mg of triamcinolone or equivalent) are allowed as needed to control joint flares during the treatment period of the study. Treated joints will not be counted for tenderness and swelling for 12 weeks post injection.

Analgesics

Analgesics and NSAIDS should be maintained at a stable dose for the duration of the study. Subjects should refrain from taking the usual morning dose of analgesics on visit days until after all clinical assessments have been completed (see Table 5.2-1 for Frequency of Assessments).

Disallowed Medications

The following medications are prohibited during the treatment period of the study:

- Any investigational agent other than CAM-3001
- Alkylating agents, including cyclophosphamide

MedImmune

CAM-3001

- Biologic agents or non-biologic DMARDS other than methotrexate
- Immunoabsorption columns, plasmapheresis and IV immunoglobulin therapy
- Live or live-attenuated vaccines

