6.4.1 Interruption or Permanent Discontinuation of Study Dosing in Individual Subjects

Interruption of dosing

MedImmune

The investigator may interrupt dosing if the subject experiences an event which, in the opinion of the investigator or the medical monitor, compromises subject safety such as active infection, deterioration of cardiopulmonary diseases meeting the exclusion criteria specified in Section 4.2.2 or the development of other complications. A subject with a neutrophil count below 1.5×10^9 /L will not receive any further investigational product until resolution of these symptoms. Similarly, a subject with a deterioration of pulmonary function (spirometry) or DLCO of more than 20% of the baseline values will not receive any further investigational product until the tests are repeated and an evaluation is performed by the pulmonologist that confirms the absence of any clinically significant lung problem. This opinion must then be communicated to the medical monitor. If the medical monitor gives approval to continue dosing, the scheduled dose should be administered at the latest within 5 days of the visit date. If dosing is not possible within 5 days, then the dose will be skipped at this visit. The next scheduled dose will be administered according to the protocol visit schedule.

Discontinuation of dosing

An individual subject will not receive any further investigational product if any of the following occur in the subject in question:

- 1) Withdrawal of consent.
- 2) Pregnancy.
- 3) Event which in the opinion of the investigator or the sponsor contraindicates further dosing such as illnesses or complications.
- 4) Any serious or life-threatening AE related to the investigational product.

MedImmune

CAM-3001

- 5) A change in concomitant RA therapy or other restricted medication during the treatment period of the study as described in Section 4.5.4.
- 6) A neutrophil count below 1.0×10^9 /L after administration of investigational product.

Subjects who are permanently discontinued from investigational product will be followed for the full study period (through Day 169). Where possible all study assessments should be completed, unless consent is withdrawn.

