7.3.1 Primary Endpoint

7.3.1.1 Efficacy

The primary efficacy objective will assess DAS28 response rates of CAM-3001 treated subjects compared with subjects who received placebo on the day of last dose of investigational product (Day 85). According to the EULAR response criteria an improvement from baseline in DAS28 of more than 1.2 would be considered a good response in subjects experiencing low disease activity (baseline DAS28 < 3.2) and a moderate response in subjects experiencing medium-to-high disease activity (baseline DAS28 \geq 3.2). A responder will be defined as a subject experiencing a decrease of more than 1.2 from their baseline DAS28 score, on the day of last dose of investigational product (Day 85).

Evaluable subjects will be cross-classified in a two-by-two contingency table according to their combined treatment group (CAM-3001 or Placebo) and by their responder status (Yes or No). The DAS28 response rate at Day 85 between combined CAM-3001 and combined placebo treatment groups will be compared using a two-sided Fisher's exact test.

Following the above comparison between the combined CAM-3001 and combined placebo treatment groups, each applicable dose cohort and the combined placebo group will be compared. These comparisons at the dose cohort level are not powered and as such their results will be considered in an exploratory setting. There will also be no adjustment for multiplicity. A 95% confidence interval of difference in DAS28 response rate between CAM-3001 and placebo treatment groups will be computed for each dose cohort to estimate the effect size of each CAM-3001 dose level.

The DAS28 response rate at Day 29 between CAM-3001 and placebo will also be compared using a Fisher's exact test.

To check the sensitivity of the comparisons, all the above analyses will be repeated over the respective cohort groupings but in the more restrictive ATP population. Due to the definition of the ATP population no imputation of the DAS28 score is needed for these analyses.

MedImmune CAM-3001 **7.3.1.2 Safety**

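### The Evaluable Population (7.2.4) re-admits early stoppers only for safety, so subjects whose dosing is stopped for poor RA control drop out of the primary Fisher test

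*Protocol*

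**What the plan says.** Four places in the protocol bear on this.

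- **7.3.1.1 Efficacy** names the set for the primary test: "Evaluable subjects will be cross-classified in a two-by-two contingency table according to their combined treatment group" and by responder status. The combined groups are then compared with a two-sided Fisher's exact test at Day 85.
- **7.2.4 Evaluable Population** gives the main entry rule: "Subjects who receive scheduled investigational product and are followed according to the protocol until Day 85 will constitute the Evaluable Population". It adds one exception for subjects who had at least one dose but "discontinue treatment prior to receiving complete treatment regimen due to safety reasons will also be included in the Evaluable Population".
- **4.5.4.1 Modification of Treatments for RA** deals with inadequate response before Day 85: "Subjects who require a change to their RA therapies for reasons other than safety, such as for poor disease control" or worsening RA, "may be discontinued from dosing upon review by the medical monitor, but will remain in the study". It then asks that the data still be collected: "All study assessments should be completed, unless consent is withdrawn".
- **6.4.1** lists among the events after which a subject receives no further product: "A change in concomitant RA therapy or other restricted medication during the treatment period of the study as described in Section 4.5.4". It follows subjects who stop permanently through Day 169.

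The only use that 7.2.2 gives for the ITT population is summarising demographic and baseline characteristics. The sensitivity analysis named in 7.3.1.1 repeats the comparisons in the According to Protocol (ATP) population, which it calls more restrictive.

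**The concern.** The endpoint is a fall in DAS28 of more than 1.2 at Day 85. A subject who needs new RA therapy because the disease is not controlled has, for practical purposes, failed on that endpoint. Under 7.2.4 a subject who stops early for an adverse event stays in the denominator, while one who stops early for inefficacy does not. Membership of the primary analysis set then depends on a post-randomisation event that is close to the outcome itself and may differ in frequency between arms.

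This is not a gap left for the SAP to fill. 7.2.4 states who is in and who is out, and 7.3.1.1 fixes that set for the primary test. The loss is also avoidable, because the protocol keeps these subjects in follow-up and asks for their assessments.

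**Working it through.** **1. Does the text exclude these subjects?** Take a subject dosed on Day 1 whose RA therapy is changed on Day 50 for poor control and whose dosing is stopped.
- Main rule of 7.2.4: the subject has not received the scheduled product to Day 85. Reading the rule as any scheduled dose would leave the safety exception with nothing to do.
- Safety exception: 4.5.4.1 describes this change as made for reasons other than safety.
- Neither route admits the subject.
- The text after 7.2.6 on last-observation-carried-forward and as-randomised classification concerns imputation and arm labels. It does not bring back a subject who is outside the set.

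**2. Reproduce the plan's power.** Inputs from 7.4: 10% placebo, 30% active, two-sided alpha 0.05, 120 active and 60 placebo evaluable. Exact power is the sum, over all pairs of counts with Fisher p ≤ 0.05, of the product of the two binomial probabilities.
- 120 v 60: 87.8% (stated 86%).
- 144 v 72: 93.6% (stated 92%).

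Both are within 2 points, so the sample size is not at fault.

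**3. Effect of exclusion under the design rates.** *Assumption:* a fraction s of each arm is stopped for poor control, and none of these subjects would have responded. The evaluable response rate is p / (1 − s).

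| Stops, active / placebo | Active | Placebo | Difference |
|---|---|---|---|
| none | 30.0% | 10.0% | 20.0 |
| 2.5% / 5% | 0.30/0.975 = 30.8% | 0.10/0.95 = 10.5% | 20.2 |
| 5% / 10% | 0.30/0.95 = 31.6% | 0.10/0.90 = 11.1% | 20.5 |

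Power depends on whether these losses are already part of the 15% dropout allowance.
- *On top of it, excluded:* 117 v 57 gives 85.8%; 114 v 54 gives 84.0%. *Kept as non-responders:* 120 v 60 gives 87.8%.
- *Within it, excluded:* 120 v 60 at the raised rates gives 87.8% and 87.7%. *Kept:* 2.5% of 144 and 5% of 72 adds about 4 and 4 subjects, so 124 v 64 at 29.8% v 9.9% gives 89.9%. 5% of 144 and 10% of 72 adds about 7 and 7, so 127 v 67 at 29.8% v 10.0% gives 90.1%.

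Keeping them is worth about 2 to 4 points of power.

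**4. Effect when the drug does nothing.** *Assumption:* true response 20% in both arms, 120 v 60 analysed.

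| Stops, active / placebo | Evaluable rates, active v placebo | Rejects for drug | Rejects for placebo |
|---|---|---|---|
| none excluded | 20.0% v 20.0% | 1.9% | 2.0% |
| 2.5% / 5% | 20.5% v 21.1% | 1.5% | 2.5% |
| 5% / 10% | 21.1% v 22.2% | 1.2% | 3.1% |
| 10% / 5% | 22.2% v 21.1% | 2.9% | 1.3% |

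The sign follows whichever arm loses more failures. Total rejection stays below 5% in every row, because Fisher's test is conservative.

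**5. Can the planned N carry a stricter rule?** Analyse all 144 v 72 randomised outside Japan and count 15% in each arm as non-responders. The rates become 0.30 × 0.85 = 25.5% and 0.10 × 0.85 = 8.5%, and exact power is 87.4%, still above 86%.

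**The case against.** The strongest reply is that the effect is small. Under the assumed rates the difference shifts by at most half a point, power stays near the plan, and if placebo fails more often the rule works against the drug. The trial is Phase 2, its primary analysis serves internal decisions, and 7.4 openly sizes it on evaluable subjects. All of that stands and limits the weight of the point. It does not justify removing failures that the protocol goes on to measure.

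The affected group is also narrower than all subjects with poor control. 4.5.4.1 says that such subjects may be discontinued after review by the medical monitor, so one kept on dosing could remain evaluable. Under 6.1.1 a significant worsening of RA can be recorded as an adverse event, so some stops might be coded as safety. This is fair, but 4.5.4.1 names worsening as non-safety, and leaving inclusion to coding is a further reason to state the rule.

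Three stronger readings are tempting, and the documents do not support them.
- *The rule inflates false efficacy claims.* That would need more poor-control stops on active than on placebo, and the protocol gives no rates by arm or reason.
- *The ATP analysis is certain to hide the problem.* 7.2.3 cites noncompliance with concomitant medications as an example of a major violation, but leaves the definitions to be documented as described in the SAP. The ATP set may drop the same subjects; the protocol does not settle it.
- *Nothing else will be done with ITT or non-responder imputation.* A SAP could add such analyses, so their absence here is not part of the point.

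**Conclusion.** The point holds as a modest, cheaply corrected design fault. By the stated rules, a subject whose dosing is stopped before Day 85 for poor RA control is removed from the primary test because of treatment failure, while one stopped for safety is kept. The case rests on avoiding outcome-related exclusion, not on lost power. The size is small under the assumed stop rates (2.5-5% active, 5-10% placebo, none of them responders): a shift of 0.2 to 0.5 points in the difference and a power cost of about 2 to 4 points. The direction of bias is unknown. It goes against the drug if placebo stops more and towards it if active stops more. All stop rates here are assumptions, since the protocol supplies none.

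**What to change.** State in 7.2.4 and 7.3.1.1 that any dosed subject who, before Day 85, stops investigational product for lack of efficacy, or whose RA therapy is changed for poor control or worsening, stays in the primary denominator as a non-responder. Both limbs are needed, because a subject can stop for lack of efficacy without any change of therapy and would otherwise still be excluded.

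The cost is a text change in two sections, with no new visits, data or subjects. Observed response rates would be slightly lower than under exclusion: by 0.8 to 1.6 points on active (30.8% or 31.6% down to 30.0%) and 0.5 to 1.1 points on placebo (10.5% or 11.1% down to 10.0%) under the assumptions above.

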7.2.5 Pharmacokinetics

The PK population is defined as all subjects who receive CAM-3001 and for whom serum concentrations of CAM-3001 are evaluable for PK data analyses. The PK population will be used to summarise all PK/PD parameters.

7.2.6 Immunogenicity

The immunogenicity population is defined as all subjects who receive at least one dose of CAM-3001 and for whom at least one serum sample for immunogenicity testing is available.

The safety and PK/PD/Immunogenicity will be presented on an as-treated basis. The analyses of disease activity endpoints as well as summaries of baseline and demographic characteristics will be presented on an as-randomised basis; ie, treatment classification will be made according to the initial randomisation regardless of whether subjects received an investigational product different from that to which they were randomised.

Last-observation-carried-forward imputation may be used in certain disease activity endpoint analyses. All other missing data will be treated as missing without data imputation.

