4.3 Treatment Assignment

An interactive web response system (IWRS) will be used for randomisation to a treatment arm and assignment of blinded investigational product kit numbers. A subject is considered randomised into the study when the investigator/designee notifies the IWRS that the subject meets eligibility criteria and the IWRS allocates the assignment of a blinded investigational product number to the subject. An interactive voice response system (IVRS) will also be available as a back-up.

Subjects will be randomised at a 2:1 ratio to receive either CAM-3001 or placebo.

The procedure for using IWRS/IVRS is as follows:

- The investigator or designee confirms that written informed consent has been obtained and that the subject meets all eligibility criteria.
- The unblinded investigational product manager will log onto the IWRS/IVRS to obtain the treatment allocation on the day indicated by the investigator/designee.
- The IWRS/IVRS assigns a treatment arm (CAM-3001 or placebo) and investigational product number(s) to the subject and then sends a confirmatory fax or e-mail with the subject identification number and investigational product number(s) is sent to the unblinded investigational product manager.

Investigational product (CAM-3001 or placebo) must be administered as soon as possible after receipt of the investigational product number. If there is a delay in the administration of investigational product such that it will not be administered on the day of receipt of the investigational product number, the MedImmune study monitor and/or its designee must be notified immediately.

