5.1.2 Clinical Pharmacology Parameters

Noncompartmental analysis will be performed for CAM-3001 treated subjects. The PK parameters to be reported include the C_{max} and AUC following the first dose, and trough concentrations following subsequent administrations. Descriptive statistics by dose cohort will be provided. If the data allow, population PK analysis will be performed.

MedImmune CAM-3001 **5.2 Schedule of Study Procedures**

All subjects who are assigned a subject identification number and receive any investigational product will be followed according to the protocol regardless of the number of doses received, unless consent is withdrawn. The investigator must notify the sponsor or designee of deviations from protocol visits or evaluations and these evaluations, if applicable, must be rescheduled or performed at the nearest possible time to the original schedule. Protocol deviations will be recorded on the source document with an explanation for the deviation. The investigator must comply with the applicable requirements related to the reporting of protocol deviations to the IRB/IEC.

Subjects will be instructed to call study personnel to report any abnormalities during the intervals between study visits and to come to the study site if medical evaluation is needed and the urgency of the situation permits. For emergency and other unscheduled visits to a medical facility other than the study site, medical records will be obtained by the investigator and made available to the sponsor or designee during monitoring visits.

A schedule of study procedures is presented in Table 5.2-1, followed by a description of each visit. A description of the study procedures is included in Section 5.3.

Evaluations	Screen		Tı	eatm	ent P	eriod	(Stu	dy Da	ys)		F	ıdy		
	Up to -28	1	4	8	15	29	43	57	71	85	88 ±2	99 ±3	113 ±7	169/ Disc ±7
VISIT	Screen	1	2	3	4	5	6	7	8	9	10	11	12	13
Written informed consent	Х													
Verify eligibility criteria	X	X												
Demographics	X													
Medical history	X													
Physical examination	X	Х										Х		Х
ECG	X													Х
TB test	X													
Chest x-ray	X													
Hepatitis A, B, C; CMV, EBV	X													
Serum βHCG	Х													

Table 5.2-1	Schedule of Subject Evaluations
--------------------	---------------------------------

Protocol MI-CP219; Amendment 3 Final

Table 5.2-1

Schedule of Subject Evaluations

	Treatment Period (Study Days)									F	ollow-i Da	up (Stı ays)	ıdy	

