Evaluations	Up to -28	1	4	8	15	29	43	57	71	85	88 ±2	99 ±3	113 ±7	169/ Disc ±7
VISIT	Screen	1	2	3	4	5	6	7	8	9	10	11	12	13
Urine βHCG		Х			Х	Х	Х	Х	Х	Х				X
INVESTIGATIONAL PRODUCT ADMINISTRATION		X			X	X	X	X	X	X				
SAFETY ASSESSMENT														
Height	Х													
Weight	Х													Х
Vital signs	Х	Х	Х	Х	Х	Х	Х	Х	Х	Х	Х	Х	Х	Х
AE/SAE assessment	Х	Х	Х	Х	Х	Х	Х	Х	Х	Х	Х	Х	Х	Х
Record concomitant medications	Х	Х	Х	Х	Х	Х	Х	Х	Х	Х	Х	Х	X	Х
Clinical chemistry, haematology with differential, platelets	Х	X			X	X	X	X	X	X		Х	Х	Х
Urinalysis	Х	Х			Х	Х	Х	Х	Х	Х		Х	Х	Х
Modified Borg scale (subjects completed) and O ₂ saturation (pulse oximetry)	х	X			X	X	X	X	X	X		X	X	X
Pulmonary Function Tests	Х	Х				Х				Х				X
PK/Immunogenicity														
CAM-3001 serum concentration		X	Х	X	X	Х		X		Х	Х	Х	Х	Х
Anti-CAM-3001 antibodies		Х				Х		Х		Х		Х	Х	X
DISEASE ACTIVITY														
Swollen joint count (66 joints)	X	X		X	X	Х	Х	X	X	X		Х	Х	X
Tender joint count (68 joints)	Х	Х		Х	Х	Х	Х	Х	Х	Х		Х	X	X
Patient assessment of pain	X	Х		Х	Х	Х	Х	Х	Х	Х		Х	X	X
Patient's global assessment of disease activity	X	X		X	X	X	X	X	X	X		Х	X	X

Protocol MI-CP219; Amendment 3 Final

	Screen	Treatment Period (Study Days)									Follow-up (Study Days)			
Evaluations	Up to -28	1	4	8	15	29	43	57	71	85	88 ±2	99 ±3	113 ±7	169/ Disc ±7
VISIT	Screen	1	2	3	4	5	6	7	8	9	10	11	12	13
Physician's global assessment of disease activity	Х	Х		Х	Х	Х	Х	х	X	Х		Х	X	Х
HAQ-DI	X	Х		Х	Х	Х	Х	Х	Х	Х		Х	Х	Х
Rheumatoid factor, anti-CCP antibodies	X	Х		Х	Х	Х	Х	Х	Х	Х		X		Х
PATIENT REPORTED OUTCOMES														
SF-36		Х				Х				Х				
FACIT-Fatigue		Х			Х	Х		Х		Х			Х	Х
MOS-sleep scale		Х				Х				Х				
CORRELATIVE STUDIES														
Receptor occupancy		Х	Х	Х	Х	Х		Х		Х	Х	Х	Х	Х
Whole blood for mRNA and miRNA analysis		X	X	X	X	X		X		X	Х	Х	Х	X
Serum for exploratory biomarker analysis		Х		Х	Х	Х		X		Х	Х	Х	X	Х
DNA Sample (optional)		Х												

Table 5.2-1 **Schedule of Subject Evaluations**

(optional) $AE = adverse event; \beta HCG = \beta$ human chorionic gonadotrophin; CCP = cyclic citrullinated peptide; CMV = cytomegalovirus; DNA = deoxyribonucleic acid; EBV = Epstein-Barr virus; ECG = electrocardiogram; FACIT = functional assessment of chronic illness therapy; HAQ-DI = Health Assessments Quesionairre-Disability Index; miRNA = micro ribonucleic acid; mRNA = messenger ribonucleic acid; MOS = Medical Outcomes Study; $O_2 = oxygen$; PK = pharmacokinetics; TB = tuberculosis; SAE = serious adverse event; SF-36 = Short Form 36

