For PK analyses, it is important that the exact time of the SC injection and of each PK sample taken is recorded for each subject. Serum samples will be collected predose at designated visit days starting with Study Day 1 for CAM-3001 level and anti-CAM-3001 antibody determination. Specific procedures for sample collection, processing, storage, and shipment can be found in a separate laboratory manual provided to sites. CAM-3001 serum concentrations and anti-CAM-3001 antibody detection will be measured using Enzyme-linked immunosorbent assay and ECL assays, respectively.

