7.3.2.2 PK and Immunogenicity

CAM-3001 serum concentrations will be summarised using descriptive statistics at each time point by treatment group. Noncompartmental PK data analysis will be performed for CAM-3001 treated subjects following the first dose, and descriptive statistics of these noncompartmental PK parameters such as C_{max} , time to maximum concentration (T_{max}), AUC and terminal half life ($T_{1/2}$), will be provided. Due to the limited sampling schedule, if

Protocol MI-CP219: Amendment 3 Final

CAM-3001 the data allow, population PK data analysis may be performed to better characterise the PK of CAM-3001 in this subject population.

Immunogenicity results will be summarised by counts and percentage of subjects who develop detectable anti-CAM-3001 antibodies by treatment group. The titre values, if available, will be summarised by cohort and time. The impact of immunogenicity on PK will be assessed if data allow.

7.3.3 **Exploratory Endpoints**

MedImmune

The potential effects of investigational product on patient-reported outcomes, and gene and protein expression will be evaluated. Associations of DNA single nucleotide polymorphisms with potential safety signals may be explored. The following exploratory analyses are among those that may be conducted.

GM-CSF-inducible gene expression and/or miRNA signature in the peripheral blood, and GM-CSFR α receptor occupancy will be used to measure the PD of CAM-3001.

The effects of CAM-3001 on levels of mRNA for GM-CSF-inducible genes will be analysed using microarray analyses and TaqMan[®] quantitative reverse transcriptase (QRT)polymerase chain reaction (PCR) assay. The miRNA profiling in the blood will be assayed using TaqMan[®] ORT-PCR. Results will be described numerically and by percent change from baseline, by treatment group and time.

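### The immunogenicity population admits only CAM-3001 recipients, so placebo subjects sampled on the same days drop out of the antibody summary and give it no concurrent background rate

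*Protocol*

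**What the plan says.** Section 7.2.6 of the protocol sets the population: "The immunogenicity population is defined as all subjects who receive at least one dose of CAM-3001", with the further condition that at least one serum sample for immunogenicity testing is available. A subject who receives only placebo cannot meet it. The same section adds: "The safety and PK/PD/Immunogenicity will be presented on an as-treated basis".

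Section 7.3.2.2 sets the summary: "Immunogenicity results will be summarised by counts and percentage of subjects who develop detectable anti-CAM-3001 antibodies by treatment group". It names no other population and does not mention placebo.

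The sampling rules cover both arms:

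- Table 5.2-1 has a row "Anti-CAM-3001 antibodies" marked at Days 1, 29, 57, 85, 99, 113 and 169, with no arm restriction.
- Section 5.3.3: "Serum samples will be collected predose at designated visit days starting with Study Day 1 for CAM-3001 level and anti-CAM-3001 antibody determination".
- Section 5.2: "All subjects who are assigned a subject identification number and receive any investigational product will be followed according to the protocol".
- Section 4.3 shows that this term covers both arms: "Investigational product (CAM-3001 or placebo) must be administered as soon as possible".

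Two nearby rules treat placebo differently. The safety population (7.2.1) takes anyone given study medication, and section 7.3.1.2 names placebo explicitly in the adverse event summaries.

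**The concern.** Immunogenicity is part of a stated secondary objective (section 2.2). A reported percentage of subjects who develop antibodies mixes true drug-induced responses with assay false positives, and each subject has six post-dose chances to test positive. A control group sampled on the same days, over the same 24 weeks and with the same assay shows how often that happens without the drug. The trial has such a group and plans to draw its blood, but the population definition keeps it out of the summary.

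The restriction suits the PK population in section 7.2.5, because placebo subjects have no drug concentrations to summarise. It suits antibody incidence less well, because a placebo subject can still give a false-positive antibody result. At stake is how a low positive percentage in a dose group is read: as a drug effect or as assay background.

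**Working it through.** There is no stated figure to reproduce; the point turns on a definition. The check counts who is excluded, then gauges what their data would tell.

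**1. Subjects excluded.** From Table 4.5.2-1, each of four cohorts has 18 placebo subjects outside Japan and 4 in Japan.

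- Placebo: 4 × (18 + 4) = 88, of whom 72 are outside Japan.
- CAM-3001: 4 × (36 + 8) = 176.
- Total: 176 + 88 = 264, matching the stated total. The table prints 38 for the 30 mg group where the abstract has 36; 38 would give 266, so 36 is used. The placebo count is unaffected.
- Scheduled placebo antibody samples: 88 × 7 = 616.

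The Japan figures assume that the local amendment, which is not shown, keeps the same sampling.

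**2. Cumulative false positives.** Let f be the per-sample false-positive rate. The protocol gives no value, so f is an assumption. With six post-dose samples taken as independent, P(at least one) = 1 − (1 − f)^6.

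| Assumed f | 1 − (1 − f)^6 | Expected among 176 CAM-3001 subjects |
|---|---|---|
| 0.1% | 0.6% | about 1 |
| 1% | 5.9% | about 10 |
| 2% | 11.4% | about 20 |

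Positive correlation between a subject's samples lowers these figures.

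**3. What the predose samples can tell.** Take the favourable case of 0 positives among 176 CAM-3001 subjects on Day 1. The one-sided 95% upper limit for f is 1 − 0.05^(1/176) = 1.7%. Carried over six samples under independence, that allows 1 − 0.05^(6/176) = 9.7% of subjects.

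**4. What the placebo group would tell.** With 0 of 88 placebo subjects positive at any post-dose visit, the one-sided 95% upper limit for the cumulative rate is 1 − 0.05^(1/88) = 3.3%. With 0 of 72, outside Japan only, it is 1 − 0.05^(1/72) = 4.1%. These limits need no assumption of independence between visits, because the cumulative rate is observed directly.

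**5. What the first-in-human study can tell.** Section 1.4 reports 32 subjects dosed once by the IV route, with every immunogenicity sample negative. If all 32 were sampled, the upper limit per subject is 1 − 0.05^(1/32) = 8.9%. The 11.4% row lies above this limit, so it is at the pessimistic end. The comparison is not exact, because the number of samples per subject in that study is not given.

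**The case against.** The strongest reply is that this is a choice and not an error. The objective concerns the immunogenicity of CAM-3001, so incidence among exposed subjects is a coherent quantity. Identical sampling in both arms may serve the blind and does not by itself commit the sponsor to tabulate placebo results. Treatment group in section 7.3.2.2 may mean the four doses, as it does in practice for serum concentrations. Section 7.2.6 does not say which summaries its population governs, section 7.1 promises listings by treatment group without excluding placebo, and table layout is normal SAP content.

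Part of this stands. A reader might infer that placebo antibody results will appear nowhere in the study report; the protocol does not say that. What does not fall away is the stated rule: the one population defined for immunogenicity cannot fill a placebo column, so an SAP that shows placebo departs from section 7.2.6 and one that follows it omits the control.

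The second reply is that the predose samples already supply the background. They do supply a per-sample rate, and counting only subjects who develop antibodies removes pre-existing reactivity. So it would be wrong to infer that the trial has no background information. The predose samples do not directly observe the cumulative rate over six later visits, or any change in the assay over time. Nothing in the protocol suggests such a change, so that part is a possibility only.

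A reader might also infer that dose groups cannot be compared without placebo. That goes too far: all doses share the same sampling days, so a constant false-positive rate affects each alike and contrasts between doses remain readable.

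**Conclusion.** The point holds as a minor one. As written, sections 7.2.6 and 7.3.2.2 leave up to 88 of 264 subjects, one third, out of the antibody summary although they are sampled on the same seven days. The post-dose percentage then has no concurrent, equally sampled background rate.

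How much this matters cannot be settled from the protocol. For assumed per-sample rates from 0.1% to 2%, the false background runs from 0.6% to 11.4% of subjects under independence, and lower with positive correlation. It would be tempting to conclude that the antibody results will be materially inflated. The protocol does not support that: it states no false-positive rate, and the only earlier evidence it gives, from a validated assay, was uniformly negative.

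The endpoint is secondary and summarised descriptively. The primary DAS28 comparison and its power are untouched.

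**What to change.** - **Section 7.2.6:** define the immunogenicity population as subjects who receive any investigational product, CAM-3001 or placebo, and have at least one immunogenicity sample. As-treated classification can stay.
- **Section 7.3.2.2:** state that placebo is shown as its own group beside each dose, using the same visits and the same positivity rule.
- **Impact of immunogenicity on PK:** keep this analysis in CAM-3001 subjects.

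The change is about a sentence in each section. The samples are already scheduled, so no extra blood draws or visits follow. The one possible cost is assaying the placebo samples, up to 616, if the sponsor had not planned to run them.
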